9.4.10 Blinding

The Investigators will have to document their assessment of the included lesion(s) in the eCRF before taking the IMD image in order not to be influenced by the IMD result. When the outcome of the IMD AI result is available the Investigator will evaluate if his/her decision would have changed if taking the result of the AI into consideration.

9.5 Investigational assessments

The investigational assessments are described in the sections below and the timing of these assessments is detailed in the schedule of events (Table 9.1, Section 9.1).

9.5.1 Demographics and other baseline characteristics

9.5.1.1 Informed consent

Signed informed consent must be obtained before any screening procedures are initiated. The informed consent procedure is further described in Section 5.3.

9.5.1.2 Demographic information

The following demographic data will be recorded: age, gender, Fitzpatrick skin type (I-IV), ethnic origin.

9.5.1.3 Medical history

Medical history relevant for the investigation, as judged by the Investigator, will be obtained, as skin cancer history.

Document	Doc. id.	Version	Page	
Clinical investigation Plan / Investigation code- AI-DSMM/	GR 21- 023	01	32 (52)	

9.5.2 Clinical performance assessments

9.5.2.1 Assessment 1

Dermoscopy image with mobile phone and attached dermatoscope

9.5.2.2 Assessment 2

The method applied according to standard of care at each site (Chaos & clues", "3- or 7-point checklist", ABCDE concept or other) for the investigator to make his/hers clinical assessment of the subjects lesions to establish whether there is a suspension of MM will be documented in the CRF.

9.5.3 Laboratory assessments

Histopathology results (PAD) from excised lesions according to standard routine.

9.5.4 Clinical safety assessments

9.5.4.1 Assessment 1

All considered reportable events in accordance with MDR, will be captured. See section below for the Serious Adverse Event (SAE) and Device Deficiency (DD).

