5 ETHICAL AND REGULATORY REQUIREMENTS

5.1 Ethical and regulatory review

Necessary approvals of the Clinical Investigational Plan (CIP), the subject Information sheet and Informed Consent Form (ICF) must be obtained before enrolment of any subject into the investigation. The written approvals, including an identification of the investigation and the date of review, will be filed in the Sponsor File and at the Investigation Site File.

It is the responsibility of the Sponsor to keep the IEC and Competent Authority informed of Serious Adverse Events (SAEs) or device deficiencies that could have led to a SAE, any substantial amendments to the CIP and any safety updates/reports during the investigational period, according to local requirements.

All correspondence with the IEC and Competent Authority will be filed both in the Sponsor Trial Master File (TMF).

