9.5.6 Safety reporting, Adverse Events and Device Deficiencies

The reporting modality for the current clinical investigation is "Pre-market clinical investigations covered by Articles 62 and 74(2) of the MDR conducted with:Non-CE marked device".

Adverse Event (AE) and Serious Adverse Event (SAE)

Template Doc. id. Version

CIP Template QMS 12-01- 02

01

Document	Doc. id.	Version	Page	
Clinical investigation Plan / Investigation code- AI-DSMM/	GR 21- 023	01	33 (52)	

- **AE** Any untoward medical occurrence, unintended disease or injury or any untoward clinical signs, including an abnormal laboratory finding, in subjects, users or other persons, in the context of a clinical investigation, whether or not related to the investigational device
- **SAE-** Any adverse event that led to any of the following:
- a) death,
- b) serious deterioration in the health of the subject, that resulted in any of the following:
 - i. life-threatening illness or injury,
 - ii. permanent impairment of a body structure or a body function,
 - iii. hospitalisation or prolongation of patient hospitalisation,
 - iv. medical or surgical intervention to prevent life-threatening illness or injury or permanent impairment to a body structure or a body function,
 - v. chronic disease,
- c) foetal distress, foetal death or a congenital physical or mental impairment or birth defect.

Device Deficiency (DD)

Is defined as any inadequacy of a medical device with respect to its identity, quality, durability, reliability, usability, safety or performance.

Device deficiencies include malfunctions, use errors, and inadequacy in the information supplied by the manufacturer including labelling.

Considered reportable events in accordance with MDR

- any SAE that has a causal relationship with the investigational device, the comparator or the investigation procedure or where such causal relationship is reasonably possible;
- any device deficiency that might have led to SAE if appropriate action had not been taken, intervention had not occurred, or circumstances had been less fortunate
- any new findings in relation to any event referred to in points a) and b)

Reporting requirements

Reportable events will be reported by the KI/RÖ or AIMT (sponsor-investigator) of the clinical investigation.

Template Doc. id. Version

CIP Template QMS 12-01- 02

01

Document	Doc. id.	Version	Page
Clinical investigation Plan / Investigation code- AI-DSMM/	GR 21- 023	01	34 (52)

Reporting timelines

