- a) All reportable events which indicate an imminent risk of death, serious injury, or serious illness and that requires prompt remedial action for other patients/subjects, users or other persons or a new finding to it Immediately, but not later than 2 calendar days after sponsor-investigator are made aware of the new event
- b) Any other reportable events or a new finding/update to it **not later than 7 calendar days** after sponsor-investigator are made aware of the new event

In the event of a reportable event, it should be documented in the subject's medical record, documented in the eCRF as well completion of the Clinical Investigation Summary Safety Report Form (appendix 13.5). The Clinical Investigation Summary Safety Report Form needs to be filled in/updated for each reportable event or for new findings/updates to already reported events. For the investigational site and during the clinical investigation, the investigator needs to report the reportable event to the sponsor immediately, but not later than 3 calendar days after investigation site study personnel's awareness of the event.

Causality assessment

The relationship between the use of the medical device and the occurrence of each adverse event shall be assessed and categorized. Each SAE will be classified according to four different levels of causality:

- 1. Not related
- 2. Possible
- 3. Probable
- 4. Causal relationship

Only causality level 1 (i.e. "not related") is excluded from reporting. If higher causality level than "not related", the event should be reported. Any device deficiency that might have led to a SAE should be reported.

Reporting form (Appendix 13.5_Clinical Investigation Summary Safety Report Form_1.0_20Jan2022

- Form is study specific and covers only the given clinical investigation
- The template form contains inserted filters and functionality to facilitate use of preferred terminology in the reporting. These are important for the analysis and should be maintained

02

Document	Doc. id.	Version	Page	
Clinical investigation Plan / Investigation code- AI-DSMM/	GR 21- 023	01	35 (52)	

 The table gives a cumulative overview of the reportable events per clinical investigation and will be updated and transmitted to participating NCAs each time a new reportable event or a new finding to an already reported event is to be reported.

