11.4 Reporting and publication of investigation results

A Clinical Investigation Report, in compliance with ISO 14155, Annex D, describing the conduct of the investigation, the statistical analysis performed and the results obtained, will be prepared by RÖ/KI.

A summarizing report will be submitted to the Competent Authorities within 12 months from end of investigation (last histopathology result received and entered in eCRF) or be available on request, as per local requirements.

If the duration of the investigation exceeds one year, the Sponsor must submit an annual safety report to the Competent Authority and to the IEC, if applicable. The report will summarize any SAEs and contain an update of the risk-benefit evaluation if there has been any change since the approval of the clinical investigation.

The aim is to prepare a scientific publication to describe the results from the clinical investigation, based on the report results.

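### Safety capture, eCRF entry and sponsor notice are written for MDR-reportable events, while Table 9.1, the causality rules in 9.5.6 and section 5.1 presuppose wider recording

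*Combined protocol and SAP*

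**What the plan says.** Two sets of provisions bear on which safety events enter the study data.

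**Provisions tied to reportable events**
- Section 9.5.4.1, the only clinical safety assessment listed, says "All considered reportable events in accordance with MDR, will be captured" and then points to the later text on SAEs and device deficiencies. The synopsis has the same phrase under its clinical safety heading.
- Section 9.5.6 defines a reportable SAE as "any SAE that has a causal relationship with the investigational device, the comparator or the investigation procedure or where such causal relationship is reasonably possible". A device deficiency is reportable if it could have led to an SAE. New findings on either kind of event also count.
- The data-entry instruction in 9.5.6 begins "In the event of a reportable event, it should be documented in the subject's medical record, documented in the eCRF". The 3-calendar-day notice from site to sponsor is likewise worded for the reportable event.

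**Provisions that are wider**
- Section 9.5.6 defines an AE as an occurrence "in the context of a clinical investigation, whether or not related to the investigational device".
- The same section states: "The relationship between the use of the medical device and the occurrence of each adverse event shall be assessed and categorized". It also has each SAE placed in one of four causality levels, the first being *not related*.
- Table 9.1 has an adverse event row marked at Visit 1 and at Follow-up 1 (from the medical record where relevant), with no restriction to reportable events. It has no row for device deficiencies.
- Section 5.1 says "It is the responsibility of the Sponsor to keep the IEC and Competent Authority informed of Serious Adverse Events (SAEs) or device deficiencies". The sentence goes on to limit the deficiencies to those with SAE potential and refers to local requirements. It sets no relatedness limit on the SAEs.

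**The concern.** The rule that decides whether an event is entered and notified depends on the causality category given to it. That category is itself a judgement which the safety data ought to let others examine. If a site follows the entry and notice instructions literally, an SAE judged *not related* need not be entered and need not be sent to the sponsor. A device deficiency judged to have no SAE potential need not be entered either. Another site, working from Table 9.1, would enter the same AE or SAE.

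Two things are at stake. First, safety data from around 30 centres may not be collected on a common rule. Second, a listing with few or no events would be hard to interpret, because it could reflect either a safe procedure or the entry rule. The synopsis presents the study as a pivotal pre-market investigation that evaluates clinical safety among other things, and 7.3 says this is the device's first test in clinical settings. For software that does not touch the subject, malfunctions and use errors, which 9.5.6 counts as device deficiencies, are among the events one would want on record.

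**Working it through.** The plan gives no AE, SAE or deficiency rate, so there is no figure to reproduce. The check is a comparison of the passages by type of event.

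1. **SAE judged at least possibly related.** It is reportable under 9.5.6, entered in the eCRF and notified within 3 days. The sections agree.

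2. **SAE judged *not related*.** It must be classified (9.5.6), falls within the adverse event row of Table 9.1, and falls within the sponsor's duty in 5.1. It is not a reportable event, so the eCRF instruction and the 3-day notice in 9.5.6 do not reach it. The sections conflict. Section 5.1 also presupposes that the sponsor knows of the event, and no route is described by which it would.

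3. **Non-serious AE.** Its relationship to the device must be assessed (9.5.6) and it falls within the Table 9.1 row, but no entry instruction covers it. The sections conflict.

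4. **Device deficiency with SAE potential.** It is reportable, entered and notified. The sections agree.

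5. **Device deficiency without SAE potential.** It meets the definition of a deficiency in 9.5.6, but has no entry instruction and no row in Table 9.1, and the deficiency wording in 5.1 does not extend to it. This is a gap rather than a contradiction. The nearest provision is 9.6.2, where the monitor checks the reporting of deficiencies without reference to seriousness.

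6. **Order of steps.** Whether an event is reportable depends on its causality or its SAE potential. An event must therefore be noted and assessed before its status is known. The plan gives no eCRF step ahead of that assessment.

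7. **Downstream use.** Section 9.7.1 lists all collected data, and 9.7.5 defines a Safety Analysis Set. Section 9.7.4 deals with incorrect diagnosis and its health-economic consequences and specifies no AE or SAE table. The safety output will therefore be whatever was entered, and no planned analysis would show that sites had applied different rules.

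**The case against.** The strongest reply is that this is loose wording and no data are lost. Section 9.5.4.1 says that reportable events are captured; it does not say that others are not. It sends the reader to 9.5.6, where every SAE has to be classified. The *not related* category is excluded there from reporting, which is not the same as exclusion from the database. Section 9.5 makes Table 9.1 govern the timing of assessments, and 9.8 requires assessments not done to be stated in the eCRF. Under 9.6.2 monitors review CRFs and source data with direct access to clinical records. The procedure is one visit with a device that does not touch the subject or alter care, and 9.7.4 names incorrect diagnosis as the main risk, which the primary endpoint captures.

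Much of this stands, and it rules out several stronger readings that a reader might infer:

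- *That unrelated SAEs are removed from the study data, so that none of them reach the eCRF.* Table 9.1 points the other way. The documents support contradictory scope, not certain loss.
- *That a single site investigator settles causality and the sponsor can never correct it.* No assessor is named, and monitoring is a partial backstop, though its extent is left to a Monitoring Plan that is not part of these documents.
- *That the plan requires every SAE to be summarised, because 11.4 says "The report will summarize any SAEs".* That sentence concerns an annual safety report due only if the study lasts more than a year. Enrolment from Q1 to Q3 2022 is at most 9 months, and histopathology takes about 2 months from excision: 9 + 2 = 11 months as planned. The report may never fall due, although 9.3.2 allows enrolment to continue until 12 melanomas are confirmed.
- *That device deficiencies are the main safety signal.* Section 9.7.4 gives that place to incorrect diagnosis. The AI code entered in the eCRF and the user questionnaire would also leave some trace of failures.

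What the reply does not answer is that the only explicit instructions on eCRF entry and sponsor notice are limited to reportable events, and that they disagree with the schedule and the causality text in the same plan.

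**Conclusion.** The inconsistency is real and should be resolved. The synopsis, 9.5.4.1 and the entry and notice text of 9.5.6 are written for reportable events. Table 9.1, the requirement in 9.5.6 to assess every AE and classify every SAE, and 5.1 presuppose more. It is therefore unclear whether SAEs judged *not related* and non-serious AEs enter the eCRF, and whether the sponsor is told of such SAEs. For device deficiencies without SAE potential there is no entry instruction at all. Sites may differ, and the safety data may contain only events already judged related.

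The size cannot be stated as a number of events, because the documents give no rate. The primary endpoint, the sample size and the accuracy estimates are not affected. The conclusion assumes that no document outside this set, such as the Monitoring Plan or the eCRF instructions, already gives a common entry rule. If one does, the plan still needs to agree with it.

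**What to change.** In the synopsis, 9.5.4.1 and 9.5.6, state that:

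- all AEs and SAEs from Visit 1 to Follow-up 1 are recorded in the eCRF with their causality category;
- all device deficiencies are recorded in the eCRF with a yes/no judgement of SAE potential;
- sites notify the sponsor-investigator of every SAE, whatever its causality category;
- the reportable-event definition governs only onward reporting to authorities.

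Add a device deficiency row at Visit 1 in Table 9.1. Leave the authority timelines as they are. No second causality assessment by the sponsor is needed for this repair, and nothing in the plan calls for one.

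The cost is wording in three places, one table row and one eCRF form, plus a modest number of extra entries and SAE notices from sites that take part without payment (11.8). No visit is added.

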9.5.5 Health economic assessments

9.5.5.1 Assessment 1

A survey will be collecting health economic related information to participating sites

9.5.6 Safety reporting, Adverse Events and Device Deficiencies

The reporting modality for the current clinical investigation is "Pre-market clinical investigations covered by Articles 62 and 74(2) of the MDR conducted with:Non-CE marked device".

Adverse Event (AE) and Serious Adverse Event (SAE)

Template Doc. id. Version

CIP Template QMS 12-01- 02

01

Document	Doc. id.	Version	Page	
Clinical investigation Plan / Investigation code- AI-DSMM/	GR 21- 023	01	33 (52)	

- **AE** Any untoward medical occurrence, unintended disease or injury or any untoward clinical signs, including an abnormal laboratory finding, in subjects, users or other persons, in the context of a clinical investigation, whether or not related to the investigational device
- **SAE-** Any adverse event that led to any of the following:
- a) death,
- b) serious deterioration in the health of the subject, that resulted in any of the following:
 - i. life-threatening illness or injury,
 - ii. permanent impairment of a body structure or a body function,
 - iii. hospitalisation or prolongation of patient hospitalisation,
 - iv. medical or surgical intervention to prevent life-threatening illness or injury or permanent impairment to a body structure or a body function,
 - v. chronic disease,
- c) foetal distress, foetal death or a congenital physical or mental impairment or birth defect.

Device Deficiency (DD)

Is defined as any inadequacy of a medical device with respect to its identity, quality, durability, reliability, usability, safety or performance.

Device deficiencies include malfunctions, use errors, and inadequacy in the information supplied by the manufacturer including labelling.

Considered reportable events in accordance with MDR

- any SAE that has a causal relationship with the investigational device, the comparator or the investigation procedure or where such causal relationship is reasonably possible;
- any device deficiency that might have led to SAE if appropriate action had not been taken, intervention had not occurred, or circumstances had been less fortunate
- any new findings in relation to any event referred to in points a) and b)

Reporting requirements

Reportable events will be reported by the KI/RÖ or AIMT (sponsor-investigator) of the clinical investigation.

Template Doc. id. Version

CIP Template QMS 12-01- 02

01

Document	Doc. id.	Version	Page
Clinical investigation Plan / Investigation code- AI-DSMM/	GR 21- 023	01	34 (52)

Reporting timelines

- a) All reportable events which indicate an imminent risk of death, serious injury, or serious illness and that requires prompt remedial action for other patients/subjects, users or other persons or a new finding to it Immediately, but not later than 2 calendar days after sponsor-investigator are made aware of the new event
- b) Any other reportable events or a new finding/update to it **not later than 7 calendar days** after sponsor-investigator are made aware of the new event

In the event of a reportable event, it should be documented in the subject's medical record, documented in the eCRF as well completion of the Clinical Investigation Summary Safety Report Form (appendix 13.5). The Clinical Investigation Summary Safety Report Form needs to be filled in/updated for each reportable event or for new findings/updates to already reported events. For the investigational site and during the clinical investigation, the investigator needs to report the reportable event to the sponsor immediately, but not later than 3 calendar days after investigation site study personnel's awareness of the event.

Causality assessment

The relationship between the use of the medical device and the occurrence of each adverse event shall be assessed and categorized. Each SAE will be classified according to four different levels of causality:

- 1. Not related
- 2. Possible
- 3. Probable
- 4. Causal relationship

Only causality level 1 (i.e. "not related") is excluded from reporting. If higher causality level than "not related", the event should be reported. Any device deficiency that might have led to a SAE should be reported.

Reporting form (Appendix 13.5_Clinical Investigation Summary Safety Report Form_1.0_20Jan2022

- Form is study specific and covers only the given clinical investigation
- The template form contains inserted filters and functionality to facilitate use of preferred terminology in the reporting. These are important for the analysis and should be maintained

02

Document	Doc. id.	Version	Page	
Clinical investigation Plan / Investigation code- AI-DSMM/	GR 21- 023	01	35 (52)	

 The table gives a cumulative overview of the reportable events per clinical investigation and will be updated and transmitted to participating NCAs each time a new reportable event or a new finding to an already reported event is to be reported.

9.6 Data quality assurance

This clinical investigation will be conducted in compliance with the CIP, relevant Standard Operating Procedures (SOPs), the principles of the European Standard EN ISO 14155 Clinical Investigation of Medical Devices for Human Subjects – Good Clinical Practice (GCP), MDR (EU) 2017/745 and any other applicable regulatory requirements.

9.6.1 CIP adherence

The Principal Investigator is not allowed to deviate from the CIP.

The Sponsor-investigator is responsible for documenting and analysing any deviations and assessing their significance. Corrective action will be implemented to avoid repeated deviations, which may include suspending the clinical investigation and/or amending the CIP.

9.6.2 Monitoring

The monitoring will be done according to the Monitoring Plan with the purpose to verify that all aspects of the CIP are complied with and that the conduct of the investigation conforms to applicable regulatory requirements and established rules for Helsinki Declaration and GCP/ISO14155, to protect the rights, safety and well-being of the human subjects.

Monitoring will be done as on-site or remote visits and during central monitoring.

During the monitoring visit the monitor will verify the Informed Consent procedure, review CRFs and source data, check SW version for the IMD, reporting of DD, etc. The extent of SDV and the strategy for risk-based monitoring will be described in the Monitoring Plan.

For the purpose of SDV, the Monitor must be given direct access to original clinical records according to the Source Data Agreement.

